**10.7 Late Occurring Adverse Events**

Refer to the instructions in the Forms Packet (or electronic data entry screens, as applicable) regarding the submission of late occurring AEs following completion of the Active Monitoring Phase (i.e., compliance with Test Schedule in Section 4.0).

**10.8 Takeda Additional Event Reporting Instructions****10.81 Special reporting requirements for Takeda (Pharmaceutical Sponsor)**

## Serious Adverse Event Definition

Serious AE (SAE) means any untoward medical occurrence that at any dose:

Results in death.

Is life-threatening (refers to an AE in which the patient was at risk of death at the time of the event. It does not refer to an event which hypothetically might have caused death if it were more severe).

Requires inpatient hospitalization or prolongation of an existing hospitalization (see clarification in the paragraph below on planned hospitalizations).

- Results in persistent or significant disability or incapacity. (Disability is defined as a substantial disruption of a person's ability to conduct normal life functions).

Is a congenital anomaly/birth defect.

Is a medically important event. This refers to an AE that may not result in death, be immediately life threatening, or require hospitalization, but may be considered serious when, based on appropriate medical judgment, may jeopardize the patient, require medical or surgical intervention to prevent 1 of the outcomes listed above, or involves suspected transmission via a medicinal product of an infectious agent.

Examples of such medical events include allergic bronchospasm requiring intensive treatment in an emergency room or at home, blood dyscrasias or convulsions that do not result in inpatient hospitalization, or the development of drug dependency or drug abuse; any organism, virus, or infectious particle (eg, prion protein transmitting Transmissible Spongiform Encephalopathy), pathogenic or nonpathogenic, is considered an infectious agent.

Clarification should be made between a serious AE (SAE) and an AE that is considered severe in intensity (Grade 3 or 4), because the terms serious and severe are NOT synonymous. The general term severe is often used to describe the intensity (severity) of a specific event; the event itself, however, may be of relatively minor medical significance (such as a Grade 3 headache). This is NOT the same as serious, which is based on patient/event outcome or action criteria described above, and is usually associated with events that pose a threat to a patient's life or ability to function. A severe AE (Grade 3 or 4) does not necessarily need to be considered serious. For example, a white blood cell count of 1000/mm^3 to less than 2000 is considered Grade 3 (severe) but may not be considered serious. Seriousness (not intensity) serves as a guide for defining regulatory reporting obligations.

AEs may be spontaneously reported by the patient and/or in response to an open question from study personnel or revealed by observation, physical examination, or other diagnostic procedures. Any clinically relevant deterioration in laboratory assessments or other clinical finding is considered an AE. When possible, signs and symptoms indicating a common underlying pathology should be noted as one comprehensive event. For serious AEs, the investigator must determine both the intensity of the event and the relationship of the event to study drug administration.

AEs which are serious must be reported to Takeda Pharmacovigilance (or designee) from the first dose of study drug through 30 days after administration of the last dose of Ixazomib. Any SAE that occurs at any time after completion of Ixazomib treatment or after the designated follow-up period that the sponsor-investigator and/or sub-investigator considers to be related to any study drug must be reported to Takeda Pharmacovigilance (or designee). In addition, new primary malignancies that occur during the follow-up periods must be reported, regardless of causality to study regimen, for a minimum of three years after the last dose of the investigational product, starting from the first dose of study drug. All new cases of primary malignancy must be reported to Takeda Pharmacovigilance (or designee).

Planned hospital admissions or surgical procedures for an illness or disease that existed before the patient was enrolled in the trial are not to be considered AEs unless the condition deteriorated in an unexpected manner during the trial (e.g., surgery was performed earlier or later than planned). All SAEs should be monitored until they are resolved or are clearly determined to be due to a patient's stable or chronic condition or intercurrent illness(es).

Since this is an investigator-initiated study, the principal investigator, [name], also referred to as the sponsor-investigator, is responsible for reporting serious adverse events (SAEs) to any regulatory agency and to the sponsor-investigator's EC or IRB.

Regardless of expectedness or causality, all SAEs (including serious pretreatment events) must also be reported in English to Takeda Pharmacovigilance (or designee):

**Fatal and Life Threatening SAEs** within 24 hours of the sponsor-investigator's observation or awareness of the event

**All other serious (non-fatal/non-life-threatening) events** within 4 calendar days of the sponsor-investigator's observation or awareness of the event

See below for contact information for the reporting of SAEs to Takeda Pharmacovigilance.

The sponsor-investigator must fax or email the SAE Form per the timelines above. A sample of an SAE Form will be provided.

The SAE report must include at minimum:

**Event term(s)**  
**Serious criteria**

- **Intensity of the event(s):** Sponsor-investigator's or sub-investigator's determination. Intensity for each SAE, including any lab abnormalities, will be determined by using the NCI CTCAE version specified in the protocol, as a guideline, whenever possible. The criteria are available online at <http://ctep.cancer.gov/reporting/ctc.html>.

- **Causality of the event(s):** Sponsor-investigator's or sub-investigator's determination of the relationship of the event(s) to study drug administration.

Follow-up information on the SAE may be requested by Takeda.

Intensity for each SAE, including any lab abnormalities, will be determined by using the NCI CTCAE version used at your institution, as a guideline, whenever possible. The criteria are available online at <http://ctep.cancer.gov/reporting/ctc.html>.

In the event that this is a multisite study, the sponsor-investigator is responsible to ensure that the SAE reports are sent to Takeda Pharmacovigilance (or designee) from all sites participating in the study. Sub-investigators must report all SAEs to the sponsor-investigator so that the sponsor-investigator can meet his/her foregoing reporting obligations to the required regulatory agencies and to Takeda Pharmacovigilance, unless otherwise agreed between the sponsor-investigator and sub-investigator(s).

Relationship to all study drugs for each SAE will be determined by the investigator or sub-investigator by responding yes or no to the question: Is there a reasonable possibility that the AE is associated with the study drug(s)?

Sponsor-investigator must also provide Takeda Pharmacovigilance with a copy of all communications with applicable regulatory authorities related to the study product(s), as soon as possible but no later than 4 calendar days of such communication.

#### 10.82 Product Complaints

A product complaint is a verbal, written, or electronic expression that implies dissatisfaction regarding the identity, strength, purity, quality, or stability of a drug product. Individuals who identify a potential product complaint situation should immediately contact Takeda and report the event. Whenever possible, the associated product should be maintained in accordance with the label instructions pending further guidance from a Takeda Quality representative.

## 11.0 Treatment Evaluation/Measurement of Effect

### 11.1 Terms and definitions

- **M-protein:** synonyms include M-spike, monoclonal protein and myeloma protein, paraprotein, M-component.

Serum M-protein level is quantitated using densitometry on SPEP except in cases where the SPEP is felt to be unreliable.

- M-proteins migrating in the  $\beta$ -region (usually IgA M-proteins)
- Cases in which the M-protein is so large and narrow on agarose (some specimens  $>4$  g/dL) that they underestimate the actual immunoglobulin level (by greater than 1500 mg/dL) due to technical staining properties of the agarose gel.
- Cases in which there are multiple peaks of same M-protein (aggregates or dimers).

If SPEP is not available or felt to be unreliable (above examples) for routine M-protein quantitation, then quantitative immunoglobulin levels derived from nephelometry or turbidometry can be accepted, with the exception that quantitative IgG may not be used. However, this must be explicitly reported at baseline, and only nephelometry can be used for that patient to assess response. SPEP derived M-protein values and quantitative nephelometric immunoglobulin values cannot be used interchangeably.

Urine M-protein measurement is estimated using 24-h UPEP only. Random or 24 h urine tests measuring kappa and lambda light chain levels are not reliable and are not recommended.

- **FLC estimation** is currently carried out using the serum FLC assay (Freelite, The Binding Site Limited, UK). Patients with kappa/lambda FLC ratio  $<0.26$  are defined as having monoclonal lambda FLC and those with ratios  $>1.65$  as having a monoclonal kappa FLC. The monoclonal light chain isotype is considered the involved FLC isotype, and the opposite light chain type as the uninvolved FLC type.

**Response terms:** The following response terms will be used: complete response (CR), Very Good Partial Response (VGPR), Partial Response (PR), Minor Response (MR), Stable Disease (SD), and Progressive Disease (PD). (APPENDIX III)

An objective status of CR is defined as (See Appendix III):

- Absence of serum monoclonal IgM protein by immunofixation
- Normal serum IgM level
- Complete resolution of extramedullary disease, i.e. lymphadenopathy and splenomegaly if present at baseline
- Morphologically normal bone marrow aspirate and trephine biopsy (*ref: Owen 2013*)
- No signs or symptoms attributable to WM

## 12.0 Descriptive Factors

12.1 Prior ibrutinib treatment at the time of registration: yes vs. no.

## 13.0 Treatment/Follow-up Decision at Evaluation of Patient

Reason Off Treatment (from the Off Treatment Form)	Go to CFU, SFU, or end folder rollout
1 = Treatment (Intervention) Completed Per Protocol Criteria	CFU

2 = Patient Withdrawal/Refusal After Beginning Protocol Therapy (Intervention)	SFU
3 = Adverse Events/Side Effects/Complications	SFU
4 = Disease Progression, Relapse During Active Treatment (Intervention)	SFU
5 = Alternative Therapy	SFU
6 = Patient Off-Treatment (Intervention) For Other Complicating Disease	SFU
7 = Death On Study	No follow-up
8 = Other	SFU
10 = Disease Progression Before Active Treatment (Intervention)	No follow-up
24 = Patient Withdrawal/Refusal Prior To Beginning Protocol Therapy (Intervention)	No follow-up

### 13.1 Continuation of treatment

Patients who are CR, VGPR, PR, MR, or SD will continue treatment per protocol.

### 13.2 Progressive disease (PD)

Treatment may continue as per treatment schema until disease progression as long as the patient continues to respond and does not have any unacceptable toxicity. Patients who develop PD while receiving therapy will go to the survival follow-up phase.

### 13.3 Off protocol treatment

Patients who go off protocol treatment for the following reasons will go to the survival follow-up phase per Section 4.2:

- Progressive Waldenstrom's macroglobulinemia at any time on the clinical trial
- Patient requests to discontinue study treatment
- Patient develops an intercurrent illness that precludes further participation, or requires a prohibited concomitant treatment
- The Investigator withdraws the patient in the patient's best interests
- Administrative reasons (e.g., the patient is transferred to hospice care)
- An adverse event, which in the opinion of the Investigator, precludes further trial participation
- A dose omission of more than 28 days beyond the scheduled date of retreatment for ixazomib and ibrutinib

All attempts should be made to complete the End of Treatment procedures if a patient goes off treatment early.

### 13.4 Clinical follow-up

If the patient has achieved CR, VGPR, PR, MR, or SD after the completion of 24 cycles of study treatment, the patient will be observed every 3 months for 2 years. After the completion of clinical follow-up, the patient will go to survival follow-up per Section 4.2 of the protocol. If the patient has progressive disease or receives subsequent treatment for Waldenstrom macroglobulinemia at any time while in clinical follow-up, the patient will go directly to survival follow-up.

### 13.5 Ineligibles

A patient is deemed *ineligible* if after registration, it is determined that at the time of registration, the patient did not satisfy each and every eligibility criteria for study entry. The patient may continue treatment off-protocol at the discretion of the physician as long as there are no safety concerns, and the patient was properly registered. The patient will go directly to the event-monitoring phase of the study (or off study, if applicable).

- If the patient received treatment, all data up until the point of confirmation of

ineligibility must be submitted. Survival follow-up will be required per the protocol.

- If the patient never received treatment, on-study material and the End of Active Treatment/Cancel Notification Form must be submitted. No further data submission is necessary.

### **13.6 Major violation**

A patient is deemed a *major violation*, if protocol requirements regarding treatment in cycle 1 of the initial therapy are severely violated that evaluability for primary end point is questionable. All data up until the point of confirmation of a major violation must be submitted. The patient will go directly to the survival follow-up phase of the study. The patient may continue treatment off-protocol at the discretion of the physician as long as there are no safety concerns, and the patient was properly registered. Survival follow-up will be required per Section 4.2 of the protocol.

### **13.7 Cancel**

A patient is deemed a *cancel* if he/she is removed from the study for any reason before any study treatment is given. On-study material and the End of Active Treatment/Cancel Notification Form must be submitted. No further data submission is necessary.

## 14.0 Body Fluid Biospecimens

### 14.1 Summary Table of Research Blood and Body Fluid Specimens to be collected for this Protocol

Research (Section for more information)	Specimen Purpose (check all that apply)	Mandatory or Optional	Blood or Body Fluid being Collected	Type of Collection Tube (color of tube top)	Volume to collect per tube (# of tubes to be collected)	Baseline	During course of treatment	End of Treatment	Process at site? (Yes or No)	Temperature Conditions for Storage /Shipping
BTK Signalosome	 Correlative  Eligibility Confirmation  Banking  Other (specify)	Mandatory	Bone marrow aspirate	Green Top tube	5 mL (2)	Baseline/ after registration but prior to treatment	After cycle 1 and then as clinically indicated*	Confirmed disease progression	No	Refrigerate
Effect of treatment on microenvironment	 Correlative  Eligibility Confirmation  Banking  Other (specify)	Mandatory	Bone marrow aspirate	Green Top tube	5 mL (1)	Baseline/after registration but prior to treatment	After cycle 1 and then as clinically indicated*	Confirmed disease progression	No	Refrigerate
Effect of treatment on microenvironment	 Correlative  Eligibility Confirmation  Banking  Other (specify)	Mandatory	Peripheral Blood	Green Top tube	5 mL (2)	Baseline/ after registration but prior to treatment	End of every 3 cycles while patient continues on treatment**	Confirmed disease progression	No	Refrigerate

\* Additional samples to be drawn if a bone marrow is done for confirmation of response or as otherwise clinically indicated.

\*\*Additional samples to be drawn in-between every 3 cycles in case there is confirmed disease progression

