bind to ITK, a member of the TEC-kinase family, which mediates TCR signaling through PLC $\gamma$ , NFAT, NF- $\kappa$ B and MAPK. This results in activation and proliferation of CD8 $+$  cells. Our hypothesis is that ibrutinib with ixazomib alters the Th2:Th1 balance in the blood and bone marrow microenvironment, skewing towards a more Th1 profile and this may translate into clinical efficacy. We further hypothesize that the robustness of the Th1 response will direct this combination's depth of response. We will assess this in bone marrow samples comparing the baseline sample to one collected after 1 cycle of treatment with ibrutinib and ixazomib using the MultiOmyx Tumor Infiltrating Lymphocytes panel for T helper (CD4 $+$ ), Treg (FOXP3 $+$ ), T cytotoxic (CD8 $+$ ), B cells (CD20 $+$ ), macrophage (CD68 $+$ ), NK cells (CD56 $+$ ), immunosuppression (PD-L1), CD138 $+$ , CD38 $+$ , ITK and BTK. Furthermore, BTK/ITK occupancy by Ibrutinib has been associated with response rates in other B-cell malignancies where this is an effective agent (CLL) but this has never been tested in WM. This assay will be performed to assess target coverage in bone marrow samples obtained from patients at the end of 1 cycle of treatment with ibrutinib and ixazomib. In addition, PBMC samples (2 ml of whole blood with heparin) from baseline and after 1 cycle of treatment will be assessed for:

Th1 cells (live $+$ , CD19 $-$ , CD3 $+$ , CD4 $+$ , CD8 $-$ , IFNg $+$ )

Th2 cells (live $+$ , CD19 $-$ , CD3 $+$ , CD4 $+$ , CD8 $-$ , IL4 $+$ )

Th17 cells (live $+$ , CD19 $-$ , CD3 $+$ , CD4 $+$ , CD8 $-$ , IL17 $+$ )

Treg cells (live $+$ , CD19 $-$ , CD14 $-$ , CD3 $+$ , CD4 $+$ , CD25 $+$ , CD127 $-$ , FOXP3, CCR4 $+$ )

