#### 4.0 Test Schedule

##### 4.1 Test schedule for Waldenström Macroglobulinemia

Tests and procedures	≤ 28 days prior to registration	≤ 14 days prior to registration	Cycle 1				Cycles 2-24 (During course of treatment) 	(End of treatment)	Clinical Follow-up
			Day 1	Day 8	Day 15	Day 22	Day 1	4 weeks after last study drug intake	Q 3 months X 2 years
Window			±3 days				±7 days		±7 days
Informed Consent	X								
Complete medical history 		X	X						
Physical exam, vital signs Wt, PS		X	X				X	X	X
Pregnancy test 		X							
Hematology group CBC w/diff		X	X	X	X	X	X	X	X
Chemistry group Sodium Chloride Potassium Magnesium Phosphate Uric acid BUN Glucose ALT/AST Alkaline phosphatase Total protein Total Bilirubin Direct Bilirubin Albumin Serum creatinine Creatinine clearance calcium		X	X	X	X	X	X	X	X

Tests and procedures	≤ 28 days prior to registration	≤ 14 days prior to registration	Cycle 1				Cycles 2-24 (During course of treatment) 	(End of treatment)	Clinical Follow-up
			Day 1	Day 8	Day 15	Day 22	Day 1	4 weeks after last study drug intake	Q 3 months X 2 years
Bone marrow aspirate and biopsy 	X						X	X	X
Electrophoresis of serum and urine (SPEP/UPEP)		X 					X 	X 	X 
Affected immunoglobulins 		X					X	X	X
Immunofixation serum and urine (IF)		X					X	X	X
Immunoglobulin free light chains (FLC)		X					X	X	X
Serum beta-2-microglobulin, LDH, serum viscosity		X					X	X	X
Tumor measurement 		X					X	X	X
EKG or ECHO or MUGA 		X					X	X	X
Adverse event monitoring		X	X	X	X	X	X	X	X
Patient Medication Diary (Appendix II) 			X				X	X	
Research Bone Marrow Aspirate Sample R (see Section 14.0)		X 					X 	X 	
Mandatory Research blood specimens (see Section 14.0) 8,R		X 					X	X	

Cycle = 28 days (except at treatment completion where cycle length will be the number of treatment days in that cycle + 28 days)

1. Does not need to be repeated on cycle 1, day 1 if completed within 5 days. A complete physical exam, including height (screening only) and weight, neurologic assessment and assessment for lymphadenopathy/organomegaly will be conducted at screening, day one of each cycle, end

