6. To be performed at screening and as clinically indicated throughout the study. Check EKG at any time if the patient's vital signs suggest an issue or if the patient has complaints that could be related to atrial fibrillation as per the physician's assessment.
7. The diary must begin the day the patient starts taking the medication and must be completed per protocol and returned to the treating institution OR compliance must be documented in the medical record by any member of the care team.
8. Blood specimens will be collected and submitted as specified in Section 14.0. Kits are required.
9. UPEP testing required at baseline only. Subsequent testing will be as needed per physician discretion.
10. Collected at registration but prior to treatment
11. After Cycle 1, Additional samples to be drawn if a bone marrow is done for confirmation of response or as otherwise clinically indicated.
12. Patient return visit requirements: Day 1 of cycles 1, 2, 3 and 4. After cycle 4, the patient may be allowed to come every other cycle (to coincide with cycle 6, 8, 10, 12, 14, 16, 18, 20, 22, 24) if considered appropriate by the treating physician. (See section 7.3)

R Research funded (see Section 19.0)

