14.23 *To explore biologic effects of Ibrutinib and Ixazomib on microenvironment in WM and correlate with response to treatment:* In cancer redirection of host immunity from a predominant Th2 to Th1 response can deliver antitumor response. Ibrutinib can bind to ITK, a member of the TEC-kinase family, which mediates TCR signaling through PLC $\gamma$ , NFAT, NF- $\kappa$ B and MAPK. This results in activation and proliferation of CD8 $+$  cells. Our hypothesis is that ibrutinib with ixazomib alters the Th2:Th1 balance in the blood and bone marrow microenvironment, skewing towards a more Th1 profile and this may translate into clinical efficacy. We further hypothesize that the robustness of the Th1 response will direct this combination's depth of response. We will assess this in bone marrow samples comparing the baseline sample to one collected after 1 cycle of treatment with ibrutinib and ixazomib using the MultiOmyx Tumor Infiltrating Lymphocytes panel for T helper (CD4 $+$ ), Treg (FOXP3 $+$ ), T cytotoxic (CD8 $+$ ), B cells (CD20 $+$ ), macrophage (CD68 $+$ ), NK cells (CD56 $+$ ), immunosuppression (PD-L1), CD138 $+$ , CD38 $+$ , ITK and BTK. Furthermore, BTK/ITK occupancy by Ibrutinib has been associated with response rates in other B-cell malignancies where this is an effective agent (CLL) but this has never been tested in WM. This assay will be performed to assess target coverage in bone marrow samples obtained from patients at the end of 1 cycle of treatment with Ibrutinib and Ixazomib. In addition, PBMC samples (2 ml of whole blood with heparin) from baseline and after 1 cycle of treatment will be assessed for:

- Th1 cells (live $+$ , CD19 $-$ , CD3 $+$ , CD4 $+$ , CD8 $-$ , IFNg $+$ )
- Th2 cells (live $+$ , CD19 $-$ , CD3 $+$ , CD4 $+$ , CD8 $-$ , IL4 $+$ )
- Th17 cells (live $+$ , CD19 $-$ , CD3 $+$ , CD4 $+$ , CD8 $-$ , IL17 $+$ )
- Treg cells (live $+$ , CD19 $-$ , CD14 $-$ , CD3 $+$ , CD4 $+$ , CD25 $+$ , CD127 $-$ , FOXP3, CCR4 $+$ ).

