**16.33 Correlative Analysis**

16.331 BTK signaling proteins (western blot and densitometric quantification) and gene expression (quantitative real-time PCR) will be examined in CD19/CD138+ WM cells collected from patients on the study. 15 protein/genes associated with BTK-signaling will be assessed and their levels from baseline samples will be compared with levels from samples during treatment. Changes over time will be evaluated using paired

sample approaches (Wilcoxon signed rank test). Baseline levels will be correlated with response (responder vs. non-responder) using Wilcoxon rank sum tests.

16.332 Exploration of the biologic effects of ibrutinib and ixazomib on microenvironment in WM will include 3 types of data:

- Immunophenotyping of tumor infiltrating lymphocytes (TILs) using the Multi-Omyx TILs platform. This will identify 17 different types of TILs from BM samples collected at baseline and then after one cycle of treatment. This data is represented as % and actual cell counts.
- Identification of 4 types of T-cells from the blood. This will be done from peripheral blood samples collected at Baseline and then after one cycle of treatment with Ixa+Ibr.
- BTK receptor occupancy: This is a competitive-binding assay essentially and will be performed in CD19+/CD138+ WM cells collected at baseline and then after one cycle of treatment with Ixa+Ibr. Readout is % occupancy

Values will be correlated with response (responder vs. non-responder) using Wilcoxon rank sum tests.

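### The Section 14.1 blood row schedules no routine draw after cycle 1, but Sections 1.52, 14.23 and 16.332 analyse that sample for aim 2.32

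*Combined protocol and SAP*

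**What the plan says.** Three places in the combined protocol and SAP fix the blood time points for the microenvironment aim (2.32), and they agree:

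- Section 1.52: "PBMC samples (2 ml of whole blood with heparin) from baseline and after 1 cycle of treatment will be assessed for" Th1, Th2, Th17 and Treg cells.
- Section 14.23 (under 14.3) repeats the plan: "from baseline and after 1 cycle of treatment will be assessed for" the same four subsets.
- Section 16.332, on the blood T-cell types: "This will be done from peripheral blood samples collected at Baseline and then after one cycle of treatment with Ixa+Ibr".

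The collection table in Section 14.1 has one peripheral blood row, labelled for the same aim and marked mandatory. It lists a baseline sample, a sample at confirmed progression, and on-treatment samples at "End of every 3 cycles while patient continues on treatment". Its footnote allows one kind of extra draw: "Additional samples to be drawn in-between every 3 cycles in case there is confirmed disease progression". The two marrow rows of the same table are worded differently: "After cycle 1 and then as clinically indicated".

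The test schedule in Section 4.1 marks research blood in the column for Day 1 of Cycles 2 to 24. Footnote 8 sends the reader elsewhere for the detail: "Blood specimens will be collected and submitted as specified in Section 14.0".

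**The concern.** Section 14.1 is the specimen collection table, so it is the natural place for a coordinator to look up when to draw research blood. The sample that the analysis section needs is not in the blood row. The marrow rows show that the table can express an after-cycle-1 sample, and the blood row does not have one.

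Blood that is not drawn at the end of cycle 1 cannot be replaced later. Without it, the blood part of 16.332 has a baseline value and no early on-treatment value. Neither the shift in Th1 and Th2 that 14.23 hypothesises nor any relation between after-cycle-1 blood values and response could then be examined in blood. A patient who stops treatment before the end of cycle 3 would contribute no routine on-treatment blood at all.

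**Working it through.** The plan gives no figure to reproduce. The check sets the places that govern blood timing side by side and counts days.

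| Place | On-treatment research blood |
|---|---|
| 1.52 | after cycle 1 |
| 14.23 | after cycle 1 |
| 16.332 | after cycle 1 |
| 14.1, peripheral blood row | end of every third cycle; otherwise only at confirmed progression |
| 4.1, research blood row | mark under Day 1 of Cycles 2 to 24, timing referred to Section 14.0 |

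**Does 4.1 settle it?** The mark covers Cycle 2 Day 1, so it permits the draw. Read literally, it would also mean a draw at every cycle, which disagrees with the 14.1 row. It defers to Section 14.0, and that section contains both the table row and 14.23, which conflict. Section 4.1 therefore adds a third possible schedule and leaves the conflict open.

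**Days.** Inputs: 28-day cycles, at most 24 of them (Sections 1.4 and 7.1), and a visit window of ±7 days for Day 1 of Cycles 2 to 24 (4.1).

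- End of cycle 1: 1 × 28 = day 28, in practice the Cycle 2 Day 1 visit.
- End of cycle 3: 3 × 28 = day 84, in practice the Cycle 4 Day 1 visit.
- Difference: 84 − 28 = 56 days.
- Closest approach with the window: latest after-cycle-1 draw 28 + 7 = 35; earliest end-of-cycle-3 draw 84 − 7 = 77; 77 − 35 = 42 days.

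No use of the window lets one draw serve as the other.

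**Draws under the 14.1 row.** 24 ÷ 3 = 8 routine on-treatment draws, at the ends of cycles 3, 6, 9, 12, 15, 18, 21 and 24. None falls after cycle 1.

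**Share of the analysis.** Section 16.332 lists three data types: marrow infiltrating lymphocytes, blood T-cells and BTK occupancy. The blood timing conflict concerns one of the three, with its 4 T-cell types.

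**Patients.** The lower bound is 0, if sites draw at Cycle 2 Day 1. The upper bound is all treated patients, if sites follow the table row. Section 16.22 caps registration at 37 + 6 + 4 = 47. The 6 apply only if the dose is de-escalated, so without that the cap is 37 + 4 = 41. The 4 include cancellations, who are never treated (13.7), so the number treated may be lower still.

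**The case against.** The best case for the plan is that one table cell is out of line with everything else. Three sections state the after-cycle-1 sample, 4.1 permits it, and footnote 8 points to Section 14.0 as a whole, which includes 14.23. The collection kits carry their own instructions (14.212), which are not in the documents and may already call for the draw. Treatment starts at only two sites (6.5).

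This argument stands as far as the consequence goes. A reader might infer that the after-cycle-1 blood will be missing throughout the trial, but the documents do not show that. The loss depends on which section the sites follow. The argument does not remove the contradiction, because the cell that is out of line sits in the collection table.

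Two further inferences should be resisted:

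- A reader might conclude that marrow timing is uniformly settled and that blood is the only loose end. The documents do not support this. In 4.1, footnotes 3 and 11 can be read as making marrow after cycle 1 conditional on clinical need, and 14.22 uses marrow at baseline and progression only. No statement about marrow consistency is made here.
- A reader might treat the absence of a named before/after test in 16.332 as an error. Section 16.332 names only a rank sum comparison of responders with non-responders and does not say which values enter it. In an exploratory analysis this is missing detail that an analyst would fill sensibly. Naming a paired test, as 16.331 does, is an optional clarification and not part of this point.

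**Conclusion.** The concern holds as an internal contradiction about research blood for aim 2.32. Three sections analyse a sample after cycle 1, and the collection table's blood row schedules no routine sample until the end of cycle 3, nominally 56 days later and never less than 42. This rests on 28-day cycles and the ±7-day window as stated, with no treatment delay.

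Confidence in the mismatch is high, because it can be read directly from the text. The extent of any data loss is undetermined, from no patients to all treated patients, because the documents do not show which instruction sites follow. At stake is one of the three data types under one exploratory aim. The primary endpoint, the interim and final decision rules and the sample size are not affected. The correction is still worth making, because an undrawn sample cannot be recovered and the change is small.

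**What to change.** Reconcile the sections. In the peripheral blood row of the Section 14.1 table, list a draw after cycle 1 (Cycle 2 Day 1) ahead of the three-cycle schedule. In Section 4.1, state that research blood follows that table, so that the mark under Cycles 2 to 24 is no longer open to an every-cycle reading.

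Cost: one extra research draw per patient of 2 × 5 mL = 10 mL, of which 14.23 needs 2 mL for the assay, and at most 47 draws in all. Over 24 cycles a patient would have 8 + 1 = 9 routine on-treatment draws. The Cycle 2 Day 1 visit is already required (4.1, footnote 12), 19.2 already funds a research marrow there, and the blood assay is already planned in 16.332.

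One loose end remains while the row is open. The ends of cycles 6, 12 and 18 correspond to Day 1 of cycles 7, 13 and 19, which are not required visits for patients who return every other cycle after cycle 4. The amended row could say how those draws are handled.
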